### **7.1.3. Clinical Laboratory Abnormalities and Other Abnormal Assessments as Adverse Events or Serious Adverse Events**

Laboratory abnormalities without clinical significance are not recorded as AEs or SAEs. However, laboratory abnormalities (eg, clinical chemistry, hematology, and urinalysis) that require medical or surgical intervention or lead to study drug interruption, modification, or discontinuation must be recorded as an AE, as well as an SAE, if applicable. In addition, laboratory or other abnormal assessments (eg, electrocardiogram, x-rays, vital signs) that are associated with signs and/or symptoms must be recorded as an AE or SAE if they meet the definition of an AE or SAE as described in Sections 7.1.1 and 7.1.2 respectively. If the laboratory abnormality is part of a syndrome, record the syndrome or diagnosis (eg, anemia), not the laboratory result (ie, decreased hemoglobin).

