However, for all subjects, study drugs should be withheld if any of the following criteria are met:

- ALT or AST > 3 x ULN AND either Total bilirubin > 2 x ULN or INR > 1.5 (in subjects not on anticoagulation)
- ALT or AST > 3 x ULN AND the appearance of fatigue, nausea, vomiting, right upper quadrant pain or tenderness, fever, rash, and/or eosinophilia (>5%)
- ALT or AST > 8 x ULN
- ALT or AST > 5 x ULN for more than 2 weeks

AND

- No other cause for the combination of laboratory abnormalities is immediately apparent (e.g. prolonged INR with warfarin use) important potential causes or contributors to abnormal AST/ALT or total bilirubin values include, but are not limited to:

— Obstructive gall bladder or bile duct disease

- Viral or alcoholic hepatitis (e.g. hepatitis A/B/C/D/E, Epstein-Barr virus, cytomegalovirus, herpes simplex virus, varicella)
- Autoimmune hepatitis
- Concomitant administration of other hepatotoxins, including excessive doses of acetaminophen, drugs that inhibit bilirubin glucuronidation (e.g. indinavir, atazanavir, irinotecan), or herbal or dietary supplements
- Hypoxic or ischemic hepatopathy or congestive hepatopathy in association with significant right-sided heart failure
- Wilson disease
- Progression of malignancy involving the liver (note that metastatic disease to the liver, by itself, should not be used as an explanation for significant AST/ALT elevations)

If study drugs are withheld, they may be reintroduced with approval from the Gilead Medical Monitor.

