7.1.6. Summaries of Adverse Events and Deaths

Treatment-emergent (TE) AEs will be summarized based on the Safety Analysis Set.

The number and percentage of subjects who experienced at least 1 TEAE will be provided and summarized by SOC, HLT, PT, and treatment group. For other AEs described below, summaries will be provided by SOC, PT, and treatment group.

- TEAEs of Grade 3 or higher (by maximum severity)
- TEAEs of Grade 2 or higher
- All TE treatment-related AEs
- TE treatment-related AEs of Grade 3 or higher (by maximum severity)
- TE treatment-related AEs of Grade 2 or higher
- All TE SAEs
- All TE treatment-related SAEs
- All TEAEs leading to premature discontinuation of study drug
- All TEAEs leading to premature discontinuation of study
- All TEAEs leading to dose temporary interruption of study drug

A brief, high-level summary of AEs described above will be provided by treatment group and by the number and percentage of subjects who experienced the above AEs. All deaths observed in the study will also be included in this summary.

Multiple events will be counted only once per subject in each summary. Adverse events will be summarized and listed first in alphabetic order of SOC and HLT within each SOC (if applicable), and then by PT in descending order of GS-0976 20 mg frequency within each SOC (HLT, if present). For summaries by severity grade, the most severe grade will be used for those AEs that occurred more than once in an individual subject during the study.

In addition to the above summary tables, TEAEs and TE treatment-related AEs will be summarized by PT only for the following, in descending order of GS-0976 20 mg frequencies:

- TE Adverse Events by Preferred Term
- Grade 3 or Higher TEAEs by Preferred Term
- Grade 2 or Higher TEAEs by Preferred Term
- TE treatment-Related AEs by Preferred Term
- Grade 3 or Higher TE treatment-Related AEs by Preferred Term
- Grade 2 or Higher TE treatment-Related AEs by Preferred Term
- All TE SAEs by Preferred Term
- All TE treatment-related SAEs by Preferred Term
- All TEAEs leading to premature discontinuation of study drug by Preferred Term
- All TEAEs leading to premature discontinuation of study by Preferred Term
- All TEAEs leading to temporary interruption of study drug by Preferred Term

In addition, data listings will be provided for the following:

- All AEs, indicating whether the event is treatment emergent
- All AEs of Grade 3 or higher
- All AEs of Grade 2 or higher
- SAEs

- Deaths

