7.2.3. Liver-related Laboratory Evaluations

Liver-related abnormalities after initial study drug dosing will be examined and summarized using the number and percentage of subjects who were reported to have the following laboratory test values listed in Section 7.2.3.1 for postbaseline measurements:

The summary will include data from all postbaseline visits up to 30 days after the last dose of study drug. For individual laboratory tests, subjects will be counted once based on the most severe postbaseline values. For both the composite endpoint of AST or ALT and total bilirubin, ALP, INR (as described below), subjects will be counted once when the criteria are met at the same postbaseline visit date. The denominator is the number of subjects in each reporting group (if applicable) in the Safety Analysis Set who have nonmissing postbaseline values of all relevant tests at the same postbaseline visit date.

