7.2.3.1. Criteria for Observation of Drug Induced Liver Injury (DILI)

For subjects with ALT (AST) baseline meeting one of the following 2 categories, close observation for DILI should be considered if the subjects meet any of the postbaseline criteria corresponding to each baseline category below.

- 1) For subjects with ALT (AST) below ULN at study baseline AND
 - meeting any of the following postbaseline criteria for liver-related events:
 - ALT (AST) $> 3 \times$ ULN at any time
 - Total Bilirubin $> 2 \times$ ULN
 - ALP $> 3 \times$ ULN
 - INR > 1.5 (except for subjects on anticoagulant therapy)
 - meeting any of the following postbaseline criteria for drug withheld:
 - ALT (AST) $> 3 \times$ ULN and Total Bilirubin $> 2 \times$ ULN

- ALT (AST) $> 3 \times \text{ULN}$ and INR > 1.5 (except for subjects on anticoagulant therapy)
- ALT (AST) $> 5 \times \text{ULN}$
- ALT (AST) $> 8 \times \text{ULN}$

2) For subjects with ALT (AST) greater than or equal to $1 \times \text{ULN}$ at study baseline AND

- meeting any of the following postbaseline criteria for liver-related events :

- ALT (AST) $> 2 \times \text{Baseline}$ at any time
- Total Bilirubin $> 2 \times \text{ULN}$
- ALP $> 3 \times \text{ULN}$
- INR > 1.5 (except for subjects on anticoagulant therapy)

- Meeting any of the following postbaseline criteria for drug withheld:

- ALT (AST) $> 3 \times \text{ULN}$ and Total Bilirubin $> 2 \times \text{ULN}$
- ALT (AST) $> 3 \times \text{ULN}$ and INR > 1.5 (except for subjects on anticoagulant therapy)
- ALT (AST) $> 5 \times \text{ULN}$
- ALT (AST) $> 8 \times \text{ULN}$

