7.2.3.2. Summaries of Criteria for Observation of DILI

The subjects who meet the criteria for close observation of DILI described in Section 7.2.3.1 will be summarized (by using number and percentage of subjects) by treatment, ALT (AST) baseline condition (whether below ULN, or greater than or equal to $1 \times \text{ULN}$), and corresponding postbaseline criteria listed in Section 7.2.3.1.

A listing will be provided for the subjects who met at least 1 of the above criteria.

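### The SAP's drug-withheld row for ALT (AST) above 5×ULN omits the protocol's more-than-two-weeks condition, so it equals or exceeds the number shown to meet that rule (small effect)

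*SAP*

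**What the plan says.** Protocol section 7.5 (Toxicity Management) gives the rule for withholding study drug. One limb is "ALT or AST > 5 x ULN for more than 2 weeks". A separate limb, above 8×ULN, needs no duration. The other limbs are above 3×ULN with raised bilirubin or INR, and "ALT or AST > 3 x ULN AND the appearance of fatigue, nausea, vomiting, right upper quadrant pain or tenderness" (the list goes on to fever, rash and eosinophilia). All limbs are joined to a further condition: "No other cause for the combination of laboratory abnormalities is immediately apparent".

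SAP section 7.2.3.1 sets out laboratory criteria for two baseline categories, ALT (AST) below ULN and at or above ULN. In each category one block is introduced by "meeting any of the following postbaseline criteria for drug withheld". That block lists above 3×ULN with bilirubin, above 3×ULN with INR, above 5×ULN and above 8×ULN. No duration is attached to the 5×ULN entry. The counting rule in SAP section 7.2.3 is: "For individual laboratory tests, subjects will be counted once based on the most severe postbaseline values". Section 7.2.3.2 then reports numbers and percentages by treatment, baseline category and criterion. No other SAP section restores the two-week condition, and section 7.7 declares no departure from the protocol's safety analyses.

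**The concern.** One result above 5×ULN puts a subject on a row headed as a withhold criterion, although the protocol's rule at that level needs more than two weeks. The SAP block itself suggests that a qualifier was lost. Without a duration, everyone above 8×ULN is already above 5×ULN, so the 8×ULN entry adds nobody to a count of subjects meeting any criterion. In the protocol the two limbs do different work: a lower level that persists, or a higher level at once.

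Safety is the primary endpoint, and liver results in a NASH trial will be read closely. A reader could take the row as the number of subjects who met the protocol's withhold rule. Protocol section 4.3 allows entry with ALT up to 5×ULN, so some subjects may start close to the threshold and cross it through ordinary fluctuation.

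**Working it through.** The plan states no figure on this point, so there is none to reproduce. The check is a comparison of the two rules, followed by a rough size.

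**1. The rules side by side**

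| Item | Protocol 7.5, withhold | SAP 7.2.3.1, drug-withheld block |
|---|---|---|
| ALT/AST >3×ULN with bilirubin or INR | yes | yes |
| ALT/AST >3×ULN with symptoms or eosinophilia | yes | absent |
| ALT/AST >5×ULN | only if more than 2 weeks | any single value |
| ALT/AST >8×ULN | at once | at once |
| No other apparent cause | required | absent |

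**2. A test case.** A subject has one ALT of 6×ULN that falls below 5×ULN within two weeks, with normal bilirubin and INR and no symptoms. No protocol limb is met. The SAP row counts the subject.

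**3. Direction.** Everyone with results above 5×ULN spanning more than 14 days has at least one value above 5×ULN. So for this row, SAP count ≥ count shown to meet the protocol limb.

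**4. Size.** The documents give no ALT distribution, so every input here is an assumption. I simulated 125 completers with no drug effect. ALT was lognormal, screening ALT was at most 5×ULN and Day 1 was a separate draw. Visits fell at random within the protocol windows (Days 8±3, 29±3, 57±3 and 85±7, and Follow-Up 28±5 days after the Week 12 visit). Follow-Up results more than 30 days after last dose were dropped, as SAP 7.2.3 requires. Documented sustained means consecutive results above 5×ULN spanning more than 14 days. The grid was median ALT 1.0 to 1.5×ULN, between-subject log SD 0.4 to 0.6 and within-subject CV 15% to 25%.

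| Assumption (median, SD, CV) | On the row | Documented sustained | Difference, of 125 |
|---|---|---|---|
| Midpoint: 1.25, 0.5, 20% | 1.1 | 0.2 | 0.9 |
| Top median: 1.5, 0.5, 20% | 2.4 | 0.6 | 1.9 |
| Highest in grid: 1.5, 0.6, 25% | 5.4 | 1.4 | 4.0 |
| Lowest in grid | below 0.1 | below 0.1 | about 0.02 |

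With no drug effect the difference follows the 2:2:1 allocation. At the midpoint it is 0.9 × 50/125 ≈ 0.4 in each active arm and 0.9 × 25/125 ≈ 0.2 on placebo. With the top median, more than four-fifths of the difference has a baseline of 3×ULN or more, and almost none of it also exceeds 8×ULN. AST, bilirubin, INR and symptoms are not modelled.

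**5. What the dated results can settle.** At their closest, scheduled visits are 15 days apart (Week 1 to 4: 26 − 11), 22 (Week 4 to 8: 54 − 32) and 18 (Week 8 to 12: 78 − 60). Two consecutive high scheduled results from Week 1 to Week 12 therefore always span more than 14 days. An isolated high result settles nothing. If Day 57 is high and Days 29 and 85 are not, the elevation may have lasted one day or anything short of 85 − 29 = 56 days. Extra tests may not help. Above a baseline of 2.5×ULN, the close-observation trigger of twice baseline lies above 5×ULN, so a value just over 5×ULN does not by itself start twice-weekly monitoring.

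**The case against.** The strongest reply is that this is a laboratory threshold table with one loose sub-heading. SAP 7.2.3 describes the output as subjects with given laboratory values, and section 7.2.3.2 names the whole set as observation criteria: "The subjects who meet the criteria for close observation of DILI described in Section 7.2.3.1 will be summarized". As a count of values above 5×ULN the row is right, and 8×ULN has its own entry. This stands as far as it goes. Leaving symptoms and cause out of such a table is defensible, but the sub-heading still says drug withheld and nothing tells the reader which terms were dropped.

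The safeguards are real. SAP 7.2.3.2 lists every subject who meets at least one criterion. Under protocol 7.1.3, laboratory abnormalities that "lead to study drug interruption, modification, or discontinuation must be recorded as an AE", and the SAP tabulates "All TEAEs leading to dose temporary interruption of study drug" along with discontinuations. ALT above 5×ULN is Grade 3 in SAP Appendix 4, so a subject with a lower baseline grade also enters the Grade 3 or 4 listing with all results for that test. This limits the harm but does not correct the summary count.

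Two stronger readings are tempting. A reader might infer that the difference is a measured over-count of transient elevations. It is not: with visits three to four weeks apart, an isolated value has unknown duration. A reader might also infer that the whole drug-withheld block over-counts. The documents do not support that, because the missing symptom limb pulls the other way and a short-lived value above 5×ULN can still meet the bilirubin, INR or symptom limb.

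**Conclusion.** The mismatch is certain from the text and its direction is certain for this one row: the count equals or exceeds the number shown to meet the protocol's 5×ULN limb. Its importance is minor. The size, roughly 0 to 4 of 125 subjects and about 1 at the grid midpoint, rests wholly on assumed ALT variability and on independent fluctuation around a fixed subject mean. It measures subjects not shown to be sustained. The lack of a difference by arm holds only because no drug effect was assumed. Neither document supports inferring that any subject would be dosed wrongly: dosing follows protocol 7.5, and the table carries no test.

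**What to change.** In SAP 7.2.3.1, for both baseline categories:

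- Keep any ALT (AST) above 5×ULN as a laboratory-threshold row, outside the drug-withheld heading.
- Under that heading, replace it with above 5×ULN documented for more than two weeks. Define this as consecutive results above 5×ULN, with none at or below it between them, spanning more than 14 days by collection date. Include unscheduled, Early Termination and Follow-Up results.
- Show any other value above 5×ULN whose duration the dated results cannot settle as duration not established. This applies to isolated values between visits as well as to a last value.
- Add a footnote that the symptom and no-other-cause terms are not applied, and that actual withholding is reported in the tables of AEs leading to interruption or discontinuation.

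Use dates and not visit counts. With last dose on Day 40 and Early Termination on Day 55, Follow-Up may fall on Day 40 + 28 − 5 = 63, only 8 days later.

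The cost is one derivation, up to two added rows per baseline category and a footnote, with no protocol change and no new data. The drawback is that the documented row can under-count. A true elevation of 20 days cannot contain two scheduled results 21 to 28 days apart, which is why the any-value row stays.

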7.2.3.2. Summaries of Criteria for Observation of DILI

The subjects who meet the criteria for close observation of DILI described in Section 7.2.3.1 will be summarized (by using number and percentage of subjects) by treatment, ALT (AST) baseline condition (whether below ULN, or greater than or equal to $1 \times \text{ULN}$), and corresponding postbaseline criteria listed in Section 7.2.3.1.

A listing will be provided for the subjects who met at least 1 of the above criteria.

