## **7.5. Toxicity Management**

Observation for Drug Induced Liver Injury (DILI):

Although subjects randomized in this study will have baseline liver disease, their hepatic function should not be significantly impaired. However, at baseline, some may have liver biochemistry levels above the upper limit of normal (ULN).

For subjects with ALT and AST below ULN at study start, close observation for DILI (as described below) should be considered in subjects with any of the following criteria (all labs confirmed by repeat testing):

- ALT or AST > 3 x ULN at any time
- Total bilirubin > 2 x ULN
- ALP > 3 x ULN
- INR >1.5 x ULN (except for subjects on anticoagulant therapy)
- Clinical signs or symptoms that are, in the opinion of the investigator, consistent with hepatitis (such as right upper quadrant discomfort, fever, nausea, vomiting, jaundice, rash, or eosinophilia > 5%)

For subjects with ALT or AST between 1 and 5 x ULN at study start, close observation for DILI (as described below) should be considered in subjects with any of the following criteria (all labs confirmed by repeat testing):

- ALT or AST > 2 x baseline at any time
- Total bilirubin > 2 x ULN

- ALP > 3 x ULN
- INR >1.5 x ULN (except for subjects on anticoagulant therapy)
- Clinical signs or symptoms that are, in the opinion of the investigator, consistent with hepatitis (such as right upper quadrant discomfort, fever, nausea, vomiting, jaundice, rash, or eosinophilia > 5%).

Close observation includes:

- Repeating liver biochemistries (ALT, AST, ALP, total bilirubin, INR) within 48 hours
- Obtaining a more detailed history of symptoms and prior or concurrent disease
- Obtaining a history of concomitant drug use (including nonprescription medications and herbal and dietary supplement preparations), alcohol use, recreational drug use, and special diets
- Obtaining a history of exposure to environmental chemical agents
- Ruling out other causes of liver disease as needed (obtain viral hepatitis panel, imaging for evaluation of biliary tract disease, etc. if required in the opinion of the primary investigator)
- Continue to monitor liver biochemistries twice weekly. Frequency can decrease to once a week or less if abnormalities stabilize or study drugs have been discontinued and subject is asymptomatic

During a period of close observation, study drugs can be continued, if desired, at the discretion of the principal investigator.

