7.7. Changes From Protocol-Specified Safety Analyses

[figure not shown]
There are no deviations from the protocol-specified safety analyses.

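### The SAP's DILI table is labelled as the protocol's close-observation criteria, but it counts unconfirmed single values and uses a different INR cut-off

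*SAP*

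**What the plan says.** Protocol 7.5 (Toxicity Management) sets close-observation rules for two groups, defined by ALT and AST at study start. In both, "close observation for DILI (as described below) should be considered in subjects with any of the following criteria (all labs confirmed by repeat testing". In both, the INR criterion is "INR >1.5 x ULN (except for subjects on anticoagulant therapy". A separate rule in the same section, on withholding study drug, uses an absolute INR: "ALT or AST > 3 x ULN AND either Total bilirubin > 2 x ULN or INR > 1.5 (in subjects not on anticoagulation".

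SAP 7.2.3.1 lists what it calls liver-related events for the same two groups. It does not mention repeat testing, and its INR criterion is "INR > 1.5 (except for subjects on anticoagulant therapy". SAP 7.2.3 gives the counting rule: "For individual laboratory tests, subjects will be counted once based on the most severe postbaseline values". SAP 7.2.3.2 then says that "The subjects who meet the criteria for close observation of DILI described in Section 7.2.3.1 will be summarized", by treatment and baseline ALT (AST) category, with a listing of everyone who met at least one criterion. SAP 7.7 adds: "There are no deviations from the protocol-specified safety analyses".

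**The concern.** The table carries the protocol's label but applies a different rule. Under the SAP one high value is enough, even if an immediate repeat is normal. A reader of the study report would take the percentage as the share of subjects who met the condition that sites were told to act on, and it is not that.

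Safety is the primary endpoint, and liver injury is the only organ-specific toxicity for which protocol 7.5 sets numerical rules. The placebo arm has about 25 subjects, and the table splits them again by baseline category, so a few chance flags can make up most of a cell. In the raised-baseline group the ALT (AST) limit is 2 x baseline. Baseline is ordinarily one value (SAP 3.8.2), so measurement noise enters on both sides of the comparison.

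**Working it through.** The plan states no figure for this table, so there is none to reproduce. The check is a comparison of text, followed by illustrations under stated assumptions.

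**1. The rules side by side (close observation only)**

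| Element | Protocol 7.5 | SAP 7.2.3 and 7.2.3.1 | Effect on the SAP count |
|---|---|---|---|
| Confirmation | Required for all laboratory criteria, both groups | None; most severe value counts | Can only raise it |
| INR | Above 1.5 x ULN | Above 1.5 | Depends on ULN |
| Clinical signs or symptoms | A criterion | Not listed | Lowers it |

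The first effect is a matter of logic: anyone with a confirmed exceedance also has a single-value exceedance.

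**2. INR.** The documents do not give the laboratory ULN. The two rules disagree for values between 1.5 and 1.5 x ULN:

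- ULN 1.0: 1.5 x 1.0 = 1.50, no gap.
- ULN 1.1: 1.65, so the SAP also counts values above 1.5 and up to 1.65.
- ULN 1.2: 1.80, so values up to 1.80.
- ULN 1.3: 1.95, so values up to 1.95.
- ULN 0.9: 1.35, so the SAP would be the stricter rule.

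**3. Confirmation, any row.** Let q be the chance of an exceedance at a visit and r the chance that a repeat confirms it, with 5 scheduled postbaseline visits (Weeks 1, 4, 8, 12 and Follow-Up) taken as independent. The SAP flags 1 - (1 - q)^5; a confirmed rule flags 1 - (1 - qr)^5. With q = 0.01 (assumed), the SAP rule gives 1 - 0.99^5 = 4.9%. The confirmed rule gives 1.5%, 2.5% and 3.9% at r = 0.3, 0.5 and 0.8.

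**4. Confirmation, the ALT > 2 x baseline row.** Simulation with no drug effect: one baseline and 5 visits, independent normal errors on the log scale, flag if visit minus baseline exceeds ln 2. The within-subject SD is an assumption. The third column keeps only subjects with an observed baseline at or above ULN, as the row requires. Its range covers a central true ALT of 1.0 or 1.5 x ULN and a between-subject log SD of 0.4 or 0.6.

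| Within-subject SD | Single value, unconditioned | Single value, baseline >= ULN | Confirmed, independent repeat (unconditioned) | Confirmed, repeat correlation 0.5 (unconditioned) |
|---|---|---|---|---|
| 0.20 | 2.9% | 1.1-2.1% | 0.4% | 0.9% |
| 0.25 | 9.1% | 3.7-6.5% | 1.8% | 3.7% |
| 0.30 | 17.0% | 7.1-12.3% | 4.5% | 8.0% |
| 0.35 | 24.7% | 10.7-17.9% | 7.8% | 13.0% |

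The third column is the relevant one. Selecting on a high observed baseline selects upward error in it, which makes doubling less likely.

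Ratios of single-value to confirmed flags, unconditioned: at correlation 0.5, from 24.7/13.0 = 1.9 to 2.9/0.9 = 3.2; at correlation 0.8, about 1.4 to 1.8. A rerun with conditioning on baseline gave about 2.2 to 4.4 and 1.5 to 2.2 respectively. Conditioning lowers the rates but not the ratios. An independent repeat gives larger ratios, but independence is implausible for a prompt re-test.

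**5. The other ALT row.** For subjects below ULN at baseline (limit 3 x ULN), the same model with central true ALT at ULN and between-subject SD 0.5 flags 0.0% to 0.9%. There is little noise to remove there. Bilirubin, ALP, AST and INR were not modelled.

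**The case against.** Protocol 7.5 guides sites on what to consider; it does not define an analysis endpoint. Protocol 8.6 specifies no DILI table. Counting any exceedance is a common and sensitive safety convention, and SAP 7.2.3 says openly that this is what it does. Flagged subjects are listed, laboratory results are listed by visit, and no formal testing is planned. The protocol's INR level is also largely recoverable elsewhere: SAP 7.2.2.3 tabulates graded abnormalities, and SAP Appendix 4 starts INR Grade 2 above 1.5 x ULN.

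Most of this stands, and it is why the any-value rows should be kept. It does not rescue the label. A sensitive screen should be presented as one, and a listing leaves the reader to reconstruct confirmation by hand.

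Stronger readings are tempting but not supported:

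- That the whole table over-counts by a fixed multiple. Only one ALT row shows appreciable noise in the model, its parameters are assumptions, and leaving out signs and symptoms works in the opposite direction.
- That noise hides a real treatment difference. Every run assumes no drug effect, and chance flags fall on all randomised arms alike.
- That SAP 7.7 is false. With no DILI table in protocol 8.6, it is not strictly contradicted.
- That the INR mismatch extends to the withholding rows. There the SAP's absolute 1.5 agrees with the protocol.

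**Conclusion.** The point holds as a mismatch between label and content. Followed as written, SAP 7.2.3.2 reports as meeting the close-observation criteria some subjects who may never have met the laboratory part of the protocol's rule. The direction of the confirmation effect is certain. The direction of the INR effect is upward only if the laboratory ULN exceeds 1.0.

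The size is not known from the documents. Under the assumptions shown, chance flags in the ALT > 2 x baseline row affect about 1% to 18% of raised-baseline subjects, and the excess over confirmed flags ranges from under 2-fold to several-fold. The within-subject SD, the repeat correlation, the ALT distribution and the INR ULN are all assumed. Trial conduct is unaffected; what changes is how a descriptive table for the primary safety endpoint can be read.

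**What to change.** In SAP 7.2.3.1 and 7.2.3.2:

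1. Keep the present close-observation rows, labelled as unconfirmed single-value exceedances.
2. Add rows counting subjects whose exceedance was confirmed by a prompt repeat of the same test, using the repeat liver biochemistries that protocol 7.5 already calls for. State the interval that counts as prompt. The next scheduled visit should not serve as the repeat: it is often about 4 weeks later, and after Week 12 it is off drug, so real transient rises would be classed as unconfirmed.
3. Show subjects with no such repeat separately; do not treat them as negative on repeat.
4. Reconcile the INR cut-off between protocol 7.5 and SAP 7.2.3.1. The documents do not settle which is intended.
5. Record any intended difference from the protocol in SAP 7.7.

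The cost is SAP wording, table shells and programming, with no new procedure for sites. The downside is a longer table and some subjects without a repeat. INR is the likeliest gap: protocol 7.5 includes it in the repeat panel, but the minimum set for an unscheduled visit (protocol 6.4.5) covers chemistry and hematology only.
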